Current/present, worst, least, and average pain at the surgical site will be assessed using a Numeric Rating Scale (NRS) as part of the Brief Pain Inventory (short form). The Brief Pain Inventory is an approved NINDS common data elements Scale. The use of single items (e.g., average pain) in addition to the composite score is supported by the IMMPACT recommendations for assessing pain in clinical trials. The NRS will be recorded at all time points (**Table 2**), ***with the primary end point being the mean value of the “average” pain scores for postoperative days 0-7*** (see statistical section for further details). The NRS is a highly-sensitive measure of pain intensity with numbers

ranging from 0 to 10, zero equivalent to no pain and 10 equivalent to the worst imaginable pain. The NRS has been demonstrated to be a valid and reliable measure following analgesic interventions. In addition, NRS scores correlate well with other measures of pain intensity, and demonstrate high test-retest reliability. These NRS characteristics led to recent IMMPACT consensus recommendations for use of the 10-point NRS of pain intensity for pain trials.

An additional instrument, the Defense and Veterans Pain Rating Scale (DVPRS), will be utilized at various time points following surgery. The DVPRS was developed specifically for—and subsequently validated in—active duty military and Veteran patient populations. Unfortunately, this new instrument has not been validated for repeated measures, and therefore will not be used as a primary end point for the current investigation. However, future pain-related investigations involving military personnel and Veterans will undoubtedly use the DVPRS, and we want the results of the current study to be comparable. Therefore, we will use the DVPRS as a secondary end point at various time points (not all to lessen the questionnaire burden on subjects).

Primary end point: *In order to claim that percutaneous PNS is superior to usual and customary analgesia, at least one of Hypotheses 1 and 2 above must be superior while the other either superior or at least noninferior.*

Hypothesis 3 (UH3): Physical and emotional **functioning** will be significantly improved in the 12 months following ambulatory surgery with percutaneous PNS as compared with usual and customary analgesia (measured with the Brief Pain Inventory).

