Throughout, the significance level will be 0.05 for each hypothesis. SAS statistical software (Cary, NC) will be used for all analyses, and East 6.0 (Cytel, Inc. Cambridge, MA) for interim monitoring and sample size calculations.

UH3 Implementation Phase sample size considerations. Sample size parameters for the implementation phase will be derived from estimates in the planning phase. The sample size calculations below are conservative in that we observed a coefficient of variation for opioid consumption observed in our preliminary data of 0.48, substantially better than the assumed 0.65. It is thus quite possible that the actual sample size for the implementation phase will be smaller.

Sample size for the full trial will be chosen to allow an overall 90% power at the 0.025 significance level (since 1-tailed tests) to claim the intervention more effective than the control on postoperative opioid requirements and pain as measured by NRS pain score. In our joint hypothesis testing on these two outcomes, we power the study to have overall 90% power to detect superiority on either

outcome and at least noninferiority on both. We assume a coefficient of variation of 1.0 for opioid consumption and a standard deviation of 2 for pain score.

Power for the joint hypothesis testing will be driven by superiority tests since superiority is needed for at least 1 of the 2 outcomes. For cumulative opioid consumption through POD 3 our previous data had a coefficient of variation (CV) of 46% (mean (SD) of 28 (13) mg). Conservatively assuming a coefficient of variation of 75% through 7 days,¹⁸³ with a total N=528 we would have 90% power to detect a relative reduction of 20% in mean opioid consumption at the overall 0.025 significance level (0.0125 for each of the two 1-tailed tests for superiority), adjusting for interim analyses (N=448 before adjustment for interim analyses).

This sample size will yield high power (>0.95%) to detect superiority based on the intervention group having 1 point or more better than the control group on NRS pain score within the first 7 days, assuming a standard deviation of 2 points for mean of the “average” pain score for each patient.

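### The fixed 0.0125 split for the two primary superiority tests is valid, but a Holm step with matching spending boundaries would add power for the second claim at no cost in patients or error

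*Combined protocol and SAP*

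**What the plan says.** All references are to section 9 of the combined protocol and SAP.

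- **Success rule** (primary end point statement after Hypothesis 2): "at least one of Hypotheses 1 and 2 above must be superior while the other either superior or at least noninferior".
- **Superiority level** (UH3 sample size considerations): the opioid calculation uses an overall level of 0.025, divided as "0.0125 for each of the two 1-tailed tests for superiority".
- **General level** (just before the sample size text): "Throughout, the significance level will be 0.05 for each hypothesis".
- **Sample size:** "with a total N=528 we would have 90% power to detect a relative reduction of 20% in mean opioid consumption", with "N=448 before adjustment for interim analyses". The opioid input is "Conservatively assuming a coefficient of variation of 75% through 7 days". For pain, the plan takes a 1-point benefit, "assuming a standard deviation of 2 points for mean of the" daily average scores.
- **Interim looks** (UH3 Implementation Phase and Figure 14): at each 25% of enrolment, with gamma -4 spending for efficacy and gamma 0 for futility. The figure caption covers superiority on either outcome.

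The 0.0125 split appears only in the sample size text. The analysis text sets out the noninferiority tests but gives no multiplicity procedure for superiority. It does not say whether enrolment continues, or what is then tested, when one outcome crosses before the other.

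**The concern.** Hypotheses 1 and 2 each predict a benefit, and the primary aim names both opioid requirements and analgesia. With a fixed split, an outcome that has already been shown superior keeps its 0.0125 for no purpose. Under the plan's own assumptions pain is the easier outcome, so opioid consumption would usually be the one held to the stricter level.

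What is at stake is whether the second outcome can be called superior or only noninferior. Whether the trial succeeds under its own rule is not affected.

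**Working it through.** **Inputs.** From the plan: opioid ratio 0.80; CV 0.75; pain difference 1 point, SD 2; 1:1 allocation; N=448 fixed, 528 with interims; four equally spaced looks; gamma(-4) efficacy spending. Assumed, because the plan does not give them: correlation between the two test statistics (0 to 0.8 examined), a smaller pain effect of 0.5 point, and no futility stop.

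**1. The plan's own figure.** SD(log) = sqrt(ln(1 + 0.75²)) = 0.668 and ln 0.80 = -0.2231. Total N = 4 × (2.241 + 1.282)² × 0.668² / 0.2231² = 445 by the normal formula, and 448 with the t-test. This matches 448. With non-binding futility the interim inflation comes to 1.187, and 448 × 1.187 = 532, close to the stated 528.

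**2. Fixed-sample gain at N=448.** Noncentrality = 0.2231 / (2 × 0.668 / sqrt(448)) = 3.535.
- At 0.0125: Φ(3.535 - 2.241) = 90.2%.
- At 0.025: Φ(3.535 - 1.960) = 94.2%.

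The second figure applies only once pain has passed. For pain at N=528 the noncentrality is 1 / (4 / sqrt(528)) = 5.74, and power at 0.0125 is 99.98%.

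**3. Boundaries** (gamma -4, looks at 25, 50, 75 and 100%):

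| One-sided level | Look 1 | Look 2 | Look 3 | Look 4 |
|---|---|---|---|---|
| 0.0125 | 3.352 | 3.038 | 2.687 | 2.299 |
| 0.025 | 3.155 | 2.818 | 2.439 | 2.014 |

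**4. Four looks, N=528, opioid -20%** (simulated correlated test statistics, one million trials per setting). Each entry is the probability of opioid superiority, fixed split to Holm:

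| Pain effect | Correlation | Continue after a crossing | Stop at first crossing |
|---|---|---|---|
| 1 point | 0 | 94.0% to 96.7% | 34.0% to 40.4% |
| 1 point | 0.3 | 94.0% to 96.7% | 33.3% to 40.7% |
| 1 point | 0.6 | 94.1% to 96.7% | 31.7% to 40.4% |
| 0.5 point | 0 | 94.0% to 96.0% | 78.8% to 82.7% |
| 0.5 point | 0.3 | 94.0% to 95.5% | 82.4% to 86.0% |
| 0.5 point | 0.6 | 94.0% to 94.8% | 87.0% to 89.9% |

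With the 0.5-point pain effect the opioid gain is therefore about 1 to 4 points. Pain gains more: about 72% to 80% if enrolment continues.

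**5. Success rule.** Holm's first step is still 0.0125 with the same boundary, so some outcome crosses under Holm exactly when one crosses under the fixed split. Success-rule power and N do not move.

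**6. Error.**
- Both nulls true: the chance of any superiority claim is 0.020 to 0.025, the same under both methods.
- Opioid null, pain effective: opioid error rises from 0.0125 to 0.025 if enrolment continues, and is at most about 0.003 if the trial stops at the first crossing.
- Opioid effective, pain null, trial stopped at the first crossing, pain then tested at a nominal 0.025 (Z = 1.96): pain error is 0.024, 0.028, 0.031 and 0.034 at correlations 0, 0.3, 0.6 and 0.8. With the 0.025-level boundary it stays below 0.01.

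**The case against.** The strongest reply is that nothing is wrong. An equal split controls the overall error, and the trial is powered for superiority on either outcome, which Holm does not alter. That stands, and it makes this an optional efficiency gain.

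A second reply is that the plan may not intend a fixed split in the analysis at all. The 0.0125 stands only in the sample size text, and a Holm plan would be sized at 0.0125 too. That also stands. It means a superiority testing rule still has to be written, more so because 0.05 for each hypothesis agrees with neither 0.0125 nor Holm.

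A third reply is that the gain depends on matters the plan leaves open: the pain effect, the correlation, and whether enrolment continues after a crossing. This is fair, and is why ranges are given. If the trial stops at the first crossing and pain benefits by 1 point, opioid superiority is missed in most trials with or without Holm, because about 86 to 91% of trials (correlation 0.6 to 0) have stopped by the second look. Holm does not cure that. The CV matters too: the sample size text also mentions 0.65 and 1.0. In a fixed sample of 528, moving from 0.0125 to 0.025 adds about 1 point of opioid power at 0.65 and about 7 points at 1.0. Only 0.75 reproduces N=448.

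The UH3 statistical section is also due for revision after the pilot. That makes the edit easy to place and does not remove the point.

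**Conclusion.** The point holds as an optional free improvement. The fixed split leaves alpha unused once one outcome is superior, and Holm recovers it within the same one-sided 0.025. At N=528 with the plan's effects, no futility stop and correlation 0 to 0.6, opioid superiority gains about 3 percentage points if enrolment continues and about 6 to 9 if the trial stops at the first crossing. With an assumed 0.5-point pain effect it gains about 1 to 4.

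A reader might infer three stronger things that the documents do not support:

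- **That the split is an error.** It is valid and consistent with the success rule.
- **That the trial could be smaller.** At one-sided 0.025 the opioid formula gives 4 × (1.960 + 1.282)² × 0.668² / 0.2231² = 377 instead of 445. This saving is not available: Holm still starts at 0.0125, and pain superiority cannot be taken as given. N=448/528 stays.
- **That the second outcome may be tested at a plain 0.025 whenever the trial stops.** At an early stop this can exceed 0.025 when the outcomes are positively correlated; the matching spending boundary is needed.

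**What to change.** In the UH3 statistical section:

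1. State Holm for the two superiority tests. Each starts at one-sided 0.0125 with its gamma(-4) boundary (Z 3.352, 3.038, 2.687, 2.299). From the look at which one outcome crosses, the other is tested against the 0.025-level gamma(-4) boundary (Z 3.155, 2.818, 2.439, 2.014), including when the trial stops at that look, and never at a nominal 0.025.
2. State whether enrolment continues after one outcome has crossed, and what is tested if it does not.
3. Replace or qualify the general statement of 0.05 for each hypothesis so that one superiority level and one multiplicity rule apply throughout.
4. Leave the noninferiority conditions, the success rule and N=448/528 as they are.

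The cost is a few sentences and a second boundary set in East. No patients are added and the overall error stays at one-sided 0.025. The rule must be fixed before anyone sees unblinded efficacy data.

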10. HUMAN SUBJECTS

Inclusion criteria: (1) Adult patients of at least 18 years of age; (2) with a planned single-injection peripheral nerve block for postoperative analgesia; and (3) undergoing one of the following surgical procedures:

- a. rotator cuff repair (shoulder)
- b. anterior cruciate ligament repair with a patellar autograph (knee)
- c. ankle arthrodesis or arthroplasty (ankle)
- d. hallux valgus correction (“bunionectomy” of the foot)

These procedures are the most painful surgeries commonly performed on an outpatient (ambulatory) basis for each of the anatomic locations (shoulder, knee, ankle, and foot), with postoperative pain requiring opioid consumption usually lasting 2 weeks.

Exclusion criteria: (1) chronic analgesic use including opioids (daily use within the 2 weeks prior to surgery and duration of use > 4 weeks); (2) neuro-muscular deficit of the target nerve(s); (3) compromised immune system based on medical history (e.g., immunosuppressive therapies such as chemotherapy, radiation, sepsis, infection), or other conditions that places the subject at increased risk; (4) implanted spinal cord stimulator, cardiac pacemaker/defibrillator, deep brain stimulator, or other implantable neurostimulator whose stimulus current pathway may overlap; (5) history of bleeding disorder; (6) antiplatelet or anticoagulation therapies other than aspirin due to the risk of bleeding with a 20-gauge insertion needle; (7) allergy to skin-contact materials (occlusive dressings, bandages, tape etc.); (8) incarceration; (9) pregnancy; (10) chronic pain of greater than 3 months of any severity in an anatomic location other than the surgical site; (11) anxiety disorder; (12) history of substance abuse; or (13) inability to contact the investigators during the treatment period, and vice versa (e.g., lack of telephone access).

Anticipated enrollment at UCSD will be 100 subjects and anticipated enrollment at all other centers will be 600 subjects, for a total of 700 subjects.

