Postoperative course. Within the recovery room following surgery, the stimulators will be attached to the leads and activated, followed by end point assessment. Subjects who had a spinal anesthetic will have end points recorded following spinal resolution. Operating and recovery room pharmacologic analgesic requirements will be recorded.

Post-hospital course. Prior to discharge, subjects and their caretakers will be provided with verbal and written stimulator/lead instructions and the telephone and pager numbers of a local investigator available at all times. Subjects will be discharged home with their leads *in situ*, and contacted every-other day by a healthcare provider until lead removal. Subjects will be also be discharged with a prescription for immediate-release oral oxycodone (5 mg tablets taken for breakthrough pain).

Therefore, *all* patients of this study—regardless of the treatment arm they are randomized to—will continue to receive current usual and customary analgesia. Subjects will be contacted by telephone for end point collection. Lead removal will occur on postoperative day 14 (+/- 2 days) by healthcare providers. If the lead is removed following Day 14, the stimulator will be turned off on Day 14 and removed subsequently. Similar to perineural catheters,¹³⁵ this procedure encompasses simply removing the occlusive dressing and gently pulling on the lead. Following study completion, the results will be mailed electronically or by the United States Postal Service to all enrolled subjects in written form using non-technical language.

Outcome measurements (end points). We have selected outcome measures that have established reliability and validity, with minimal inter-rater discordance, and are recommended for pain-related clinical trials by the World Health Organization and the Initiative on Methods, Measurement, and Pain Assessment in Clinical Trials (IMMPACT) consensus statement.¹³⁶ Importantly, nearly all outcome measures are common data elements from the National Institute of Neurological Disorders and Stroke (NINDS).¹³⁷ End points (Table 2) will be evaluated at baseline (prior to surgery on postoperative day 0), during the treatment period (postoperative days 1-14); and the follow-up period (postoperative day 15 and months 1, 4, and 12).

Table 2. Summary of post-enrollment assessments (color added for clarity)

Time Point:	Postoperative Days								Postoperative Months		
	0	1	2	3	4	7	11	15	1	4	12

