Opioid consumption previous 24 h	•	•	•	•	•	•	•	•	•	•	•
Average Pain [NRS]	•	•	•	•	•	•	•	•	•	•	•
Worst Pain [NRS]	•	•	•	•	•	•	•	•	•	•	•
Brief Pain Inventory, Short Form	•			•		•		•	•	•	•
Defense and Veterans Pain Rating Scale	•			•		•		•	•	•	•
World Health Organization Quality of Life Instrument	•								•	•	•
Post-Traumatic Stress Disorder Checklist (C)	•										
Masking Assessment		•									

Demographic and medical history. Subjects will have demographic and anthropomorphic data collected based on NINDS case report form General Core and Demographics Modules and Guidelines, including age, sex, height, weight, educational level, employment status, marital status, and U.S. military service (e.g., none, discharged, active). In addition, the medical history based on the common data elements of the NINDS Medical, Family, Behavioral History, History of Disease/Injury Event, and Prior and Concomitant Medications Sub-Domains will be collected, and include the mechanism of original injury, medications (including analgesics), previous surgical procedures, comorbidities, existing sensory deficits of the target nerve distribution, preoperative pain levels measured on a Numeric Rating Scale for pain (including daily least, average, worst and current), and muscle strength if applicable (measured with a pressure transducer; **Table 1**). In addition, since post-traumatic stress disorder (PTSD) may be associated with the severity of pain,¹³⁸ at baseline we will apply the PTSD Checklist (PCL-C), a 20-item self-report measure reflecting symptoms of PTSD validated in military,¹³⁹ Veteran,¹⁴⁰⁻¹⁴² and civilian populations.¹⁴³

Postoperatively, surgical endpoints will be recorded such as surgical duration, tourniquet duration (if applicable), analgesic administration, anesthetic administered, and any sedative agents provided. In addition, subjects will have baseline end points measured including a pain score at the surgical site using the Numeric Rating Scale (NRS, 0-10). **The remaining end points of Table 2 are described in detail under each Hypothesis in the UH3 Implementation Phase section description below.**

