Quarterly Total:	0	0	0	0	32	32	0	0	48	48	48	48	48	48	48	48	48	48	48	0	0	0	0	592	
Yearly Total:	0				64				192				192				144				0				

The Study Team (Figure 13). The study team consists of the Principal Investigator, 7 additional members of the Steering Committee, 7 Site Directors, 1 research coordinator for each of the 7 enrolling centers, and 2 Significant Contributors from the company that developed the electrical leads and stimulator.

Statistical Plan and Data Analysis

Randomized groups will be compared for balance on baseline characteristics using descriptive statistics and the standardized difference (i.e., difference in means or proportions divided by pooled standard deviation). Absolute standardized differences larger than 0.10 will be considered imbalanced and the corresponding variables considered for adjustment in all analyses. Primary analyses will be modified intent-to-treat, such that all randomized patients who receive at least some of the study intervention will be included in the analyses. All patients will be analyzed in the group to which they were randomized.

Statistical methods will largely be the same for the Planning Phase and the Implementation Phase. As explained below, one difference is that in the planning phase focus we will be on the estimated confidence interval for the treatment effects and the variability of the outcomes, as these will be used in designing the full trial. Another is that interim analyses and more thorough subgroup analyses will be done in the Implementation Phase. Details are given below.

UG3 Planning Phase. For Specific Aim 2 we will estimate the treatment effect of PNS versus usual and customary care on pain and opioid consumption using a joint hypothesis testing framework. Specifically, we will conclude PNS is superior to usual and customary analgesia, at least one of Hypotheses 1 and 2 must be superior while the other either superior or at least noninferior.

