We will first test for noninferiority of PNS to usual care on each of the two outcomes using 1-tailed noninferiority tests. The noninferiority deltas will be 1 point (worse) in pain score and 20% higher in opioid consumption. Noninferiority will be assessed at the overall 0.05 significance level with no adjustment to the significance criterion for testing two outcomes since noninferiority is required on both outcomes – i.e., an intersection union test. A noninferiority delta of 1 point in pain score is conservative since receiver operating characteristic curve analysis has demonstrated that changes from baseline of at least 1.7 along a 10-point NRS accurately identified patients who rated improvements as “much improved” or more, compared with those who perceived no change or worsening following analgesic interventions.^{153,156,177-179}

We will assess noninferiority on pain score using a one tailed t-test which incorporates the noninferiority delta of 1 point. The estimated treatment effect for pain score will be derived from a linear mixed effects model with the outcome of patient’s “average” pain score for each day, with fixed effects for intervention (PNS vs usual care) and time (days 1 through 7), and assuming an autoregressive correlation structure among and measurements on the same patient overtime. We will then test for noninferiority with a one tailed t-test in which the numerator is the estimated treatment effect from the model minus the noninferiority delta (1), and the denominator is the standard error of the estimated treatment effect. This method will yield results similar to comparing groups on the patient mean of these seven days, but is more flexible since it allows for missing data and also directly accounts for the correlation within patient. The model also allows assessing the treatment by time interaction, but this will most likely not be of interest.^{180,181}

Cumulative opioid consumption is not typically normally distributed, but usually approximates a log-normal distribution. We therefore plan to assess the treatment effect of PNS versus usual care on the log transformed cumulative consumption through POD 7 using a simple linear regression model (equivalent to a t-test). The estimated treatment effect (i.e., difference between groups) will then be used in a noninferiority test with null and alternative hypotheses as: $H_0: \mu_1 - \mu_2 \geq \log(1.2) =$

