Planning Phase sample size considerations. The sample size for the planning phase of 64 patients will be sufficient to estimate the treatment effects of interest with moderate precision, i.e., a confidence interval width of roughly 1.1 standard deviations for each outcome measure. Confidence interval width for a standard deviation estimate will be 0.70 standard deviations. The planning phase will be sufficient to use in estimating the expected treatment effect and standard deviation for each outcome for the larger trial.

UH3 Implementation Phase. Statistical methods for the UH3 Implementation Phase will follow very closely the methods described for the UG3 Planning Phase. The main difference is that UH3 Implementation Phase will have sufficient data to conduct the subgroup analyses and also considerably more power to assess the treatment effects of interest.

Another substantive difference from the planning phase is that in the full trial we will conduct interim analyses at each 25% of the planned enrollment using a group sequential method with gamma spending function and gamma parameter of -4 (quite conservative) for efficacy and 0 (moderately aggressive) for futility (**Figure 14**). The probability of crossing a boundary for either efficacy (mainly) or futility at the first through fourth looks would be 0.10, 0.42, 0.80 and 1.0, respectively, assuming the alternative hypotheses were true.

Figure 14. Stopping boundaries for 1-tailed tests for superiority for either pain score or opioid consumption. Blue region indicates superiority (reduced opioid consumption or pain score) and pink region indicates futility (lack of superiority). Z-statistic represents strength of evidence against the null hypothesis, either ratio of means or difference in means divided by standard error.

Missing outcomes data will be summarized along with the etiology of the absence. | While very little outcomes data is expected to be missing,

analyses will be intention to treat, and imputation of missing data using methods such as multiple imputation and last observation carried forward will therefore be utilized, based on the situation. In a conservative analysis imputation will involve the conservative approach of assigning the worst observed outcome to patients in intervention groups and best observed outcomes to those in control.

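### Some preoperative opioid users can enrol, yet the primary opioid regression does not prespecify the recorded preoperative use as a covariate; the cost is precision only, and it may be small

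*Combined protocol and SAP*

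**What the plan says.** Section 10, exclusion criterion (1), removes patients with "chronic analgesic use including opioids (daily use within the 2 weeks prior to surgery and duration of use > 4 weeks". The two conditions are joined by a conjunction, so a patient who meets only one of them is eligible.

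Section 9 records prior use in two places. The history covers "medications (including analgesics". Table 2 lists "Opioid consumption previous 24 h" at every time point including day 0, and the paragraph on outcome measurements says of these assessments: "End points (Table 2) will be evaluated at baseline (prior to surgery on postoperative day 0".

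The statistical plan analyses log cumulative consumption through postoperative day 7 "using a simple linear regression model (equivalent to a t-test". Treatment is the only term described. The full trial inherits this: "Statistical methods for the UH3 Implementation Phase will follow very closely the methods described for the UG3 Planning Phase".

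The one route by which a baseline variable can enter is the balance check that opens the statistical plan: "Absolute standardized differences larger than 0.10 will be considered imbalanced and the corresponding variables considered for adjustment in all analyses". The planned subgroups are gender, ethnicity and anatomic location; prior opioid use is not among them.

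**The concern.** Preoperative use is the baseline counterpart of the opioid endpoint. If users consume more after surgery than non-users, leaving the variable out puts that difference into the error term of the opioid superiority test and of the opioid noninferiority test. The second matters because any overall claim needs noninferiority on both outcomes.

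The balance check does not do the same job, for three reasons. It responds to chance imbalance and not to prognostic strength. It commits the analyst only to consider adjustment. And it depends on the data, so with interim analyses at each 25% of enrolment the model could differ between looks.

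**Working it through.** **Inputs from the documents** (Section 9, UH3 sample size considerations and interim plan): 20% reduction in opioid consumption, CV 75%, one-sided 0.0125 per outcome, 90% power, N=448 before and 528 after interim adjustment, 1:1 allocation, four looks with gamma -4 for efficacy and 0 for futility.

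**1. Reproduce the plan's sample size.**
- Log effect: |ln 0.8| = 0.2231.
- Log variance: ln(1 + 0.75²) = 0.4463, so SD = 0.668.
- n per arm = 2 × 0.4463 × (2.2414 + 1.2816)² / 0.2231² ≈ 223, or 446 in total. The t-based version gives 447.5, i.e. 448.
- The four-look design with non-binding futility has an inflation factor of 1.182, giving 527 to 530 against the stated 528.

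The same section also mentions CVs of 0.65 and 1.0. These would give 352 and 692, so 0.75 is the value behind 448. The stated power therefore comes from an unadjusted log-scale test and relies on no covariate.

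**2. How often the balance check would select prior use.** With 264 per arm and simple randomisation, the standardised difference has standard error √(2/264) = 0.0870. Then P(|difference| > 0.10) = 2 × [1 − Φ(0.10/0.0870)] = 2 × [1 − Φ(1.149)] = 0.25. The same formula at N = 132, 264 and 396 gives about 0.57, 0.42 and 0.32.

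**3. What always adjusting would gain.** Two inputs are assumptions, because the documents do not give them: the share of users p, and the ratio r of users' to non-users' consumption. CV 0.75 is taken as the total variation.
- Variance explained: R² = p(1 − p)(ln r)² / 0.4463.
- Fixed-design power at 448: Φ[0.2231 / (0.668 × √(1 − R²) × √(2/224)) − 2.2414].
- Unadjusted: Φ(3.535 − 2.241) = 0.902.
- At p = 0.10 and r = 2: R² = 0.09 × 0.4805 / 0.4463 = 0.097, and power = Φ(3.720 − 2.241) = 0.930.

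The group-sequential column uses the four-look boundaries. Equivalent N is 528/(1 − R²).

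| p | r | R² | Power, fixed 448 | Power, four looks at 528 | Equivalent unadjusted N |
|---|---|---|---|---|---|
| none | – | 0 | 0.902 | 0.902 | 528 |
| 0.05 | 1.5 | 0.017 | 0.907 | 0.907 | 537 |
| 0.10 | 2 | 0.097 | 0.930 | 0.929 | 585 |
| 0.20 | 2.5 | 0.301 | 0.977 | 0.973 | 755 |

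**4. Whether the covariate is cleanly separate from the outcome.** The paragraph on outcome measurements places the day-0 assessment before surgery, while Hypothesis 1 defines the endpoint as the cumulative dose for days 0-7. The postoperative course also has end points assessed in the recovery room. As written, the day-0 item could be read as baseline, as outcome, or as both.

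**The case against.** The strongest reply is that nothing here is broken. Randomisation protects the comparison and type I error is unaffected. The assumed CV already contains any variance due to prior use, and 448 and 528 deliver 90% power unadjusted. The preliminary CVs of 0.46-0.48 are well below 0.75 (the 0.46 is through day 3 only); at 0.48, unadjusted fixed-design power at 448 would be about 0.998. The pilot is also meant to revise the statistical section. All of this stands, and it limits the point to precision. It does not justify leaving out a recorded baseline variable, particularly as the protocol expects the pilot to reduce the sample size.

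It is also fair that the size rests on assumed inputs. The top row of the range pairs the highest share with the highest dose ratio. Excluding chronic pain elsewhere and a history of substance abuse may leave few users.

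A reader might infer that the plan ignores prior use altogether. It does not, because the balance check allows adjustment in all analyses.

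A reader might also infer that continuing preoperative use pulls the treatment ratio toward 1 and lowers power. The documents do not support this. They describe the recorded outcome as oxycodone tablets and do not establish that continuing preoperative opioids are counted. They do not say that stimulation leaves such use unchanged. The 20% reduction is the planned effect in the population enrolled. Nor would a main-effect covariate restore a diluted ratio.

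Finally, this is one instance of a wider gap, since the described model omits the stratification factors too. That is true, but it does not remove the case for this covariate.

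**Conclusion.** The point holds as a matter of precision. Eligibility admits some preoperative opioid users, their use is recorded, and the primary opioid regression has no prespecified place for it. The discretionary screen would pick it up by chance in about one full trial in four.

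Under the stated assumptions, prior use explains about 2-30% of log variance. In the middle case it explains about 10%, and power moves from about 0.90 to 0.93, which is worth roughly 57 extra unadjusted subjects (585 − 528). In the low case the gain is half a percentage point. The true position depends on the share of users and their relative dose, neither of which is given, and it may be near the low end.

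The plan should not be read as biased, underpowered or exposed to a higher type I error on this account.

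**What to change.** In the primary log-opioid regression, prespecify preoperative opioid use (any versus none) as a fixed covariate for both the superiority and the noninferiority test, at every look and regardless of observed imbalance. Define it from the medication history together with the pre-surgery day-0 item, because a 24-hour item alone would miss intermittent users. State that opioid intake before surgery is baseline and is not counted in the days 0-7 cumulative dose.

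A treatment-by-prior-use estimate may be reported, but as descriptive only, since it would have little power. For illustration, take 10-20% users with 30-50% of their dose unaffected by treatment. The log-ratio difference is ln[b + 0.8(1 − b)] − ln 0.8 = 0.072 to 0.118 for b = 0.3 to 0.5, and its standard error is 0.668 × √(2/264) × √(1/p + 1/(1 − p)) = 0.194 to 0.145 for p = 0.10 to 0.20. Two-sided 5% power is then about 7% to 13%.

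The cost is SAP wording and one degree of freedom. The data are already collected, and eligibility and conduct do not change. The revision of the statistical section already planned after the pilot is a natural time to make the change.
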